10.3 Reports of severe depression, suicidality, or homicidality

The participant surveys contain multiple items asking about participant activity, behavior, and health (including a standard 8-question section used to monitor the severity of depression). It is possible that during survey administration (or during other project-related activities [e.g., DSME group classes, 1-on-1 encounters, etc.]), participants will reveal symptoms of major depression that could include disclosure of suicidal / homicidal thoughts, plans, and risks. While food bank and project staff may not have expertise in the treatment of mental health emergencies, it is critical that project staff is skilled in identifying potential risks and responding appropriately to protect participants' and others' well-being. This section describes how to handle possible mental health emergencies identified during study activities.

All food bank sites and partner pantries should maintain a list of local mental health resources for staff reference and to be provided to any participant who suggests severe depression and/or depression with suicidal or homicidal thoughts.

Suicidal Ideation Protocol

Suicidal ideation (SI) refers to a person's thoughts about or a preoccupation with suicide. The range of suicidal ideation varies greatly from fleeting thoughts, to extensive thoughts, to detailed planning, role playing (e.g., standing on a chair with a noose), and incomplete attempts. Study staff should be attentive to study participants who may exhibit any variation of SI.

If during a study activity a participant reports suicide ideation, study staff should immediately ask this question to ascertain intent:

- “I am so sorry you feel this way. For your safety, I have to ask a difficult question: do you have a plan to act on these thoughts to harm yourself?”
- If a participant answers “no” (**no intent**)
 - Staff should respond: “I am so sorry you feel this way, but I am glad you do not have plans to harm yourself. If you remember from the consent form, having thoughts of harming yourself, even if you won't act on them, is a reason that I need to contact [name] (the doctor in charge of this study), your doctor or your doctor's team. We do this to make sure you are safe. Before we continue with the survey / activity, please give me a minute to speak with a doctor who may be able to help you.”
 - Staff should contact participant's primary care provider or provider's clinic to have PCP assess participant over the phone.
 - If participant does not have a PCP (or does not know the name of the provider or of their health care clinic), study staff should contact [name] at [contact] (pager) or on her cell at [contact] to report incident and have her assess the participant over the phone.
 - If participant's PCP, other clinic provider, or [name] is able to speak with the client and confirms the client has no intent, proceed with survey. Document event in MS Access database.

- If participant's provider, clinic, or [name] is unable to speak with client, staff should contact local community health clinic or local mental health resource to have other trained professional assess participant. If medical/mental health professional is able to speak with the client and confirms the client has no intent, proceed with survey. Document event in MS Access database.
 - If the contacted medical professional identifies intent to harm, follow any physician instructions, stop study activity, do not leave participant alone, and call 911 to activate the local emergency response system (see below).
 - Page [name] at [contact] or on her cell at [contact] to report incident.
 - Document event in detail; include report in MS Access database for study participants.
- If a participant answers "yes" (**has intent**)
 - Staff should respond: "I am so sorry you are feeling this way, and I am very concerned you might harm yourself. If you remember from the consent form, if you report you may harm yourself I will need to contact your doctor or other medical professional. We want to make sure you get the help you need to keep you safe. I apologize, but I need to stop this survey/activity now. Please give me a moment to speak with a doctor who can help you."
 - Stop survey administration or study activity immediately.
 - Do NOT leave participant alone; ask participant if another study staff person or food bank staff person can sit with them for a few minutes.
 - Call 911 to report a mental health emergency; inform operator of situation, your location, and the participant's disclosure of SI with intent.
 - Stay with client until emergency medical response arrives to evaluate participant
 - Page [name] at [contact] or on her cell at [contact] to report incident.
 - Document event in detail; include report in MS Access database for study participants.

The primary investigator must be made aware of any emergencies involving study participants as soon as possible.

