7.6 Survey Administration

This section of the MOP covers instructions for the administration of surveys used in the course of this study. Surveys are administered by trained FAITH-DM research staff to consented food bank clients in the participant’s preferred language. All surveys will be administered via the CASIC data collection software on a laptop provided by University of California San Francisco.

This study includes a baseline survey and two follow-up surveys. All participants will complete the same Baseline Survey (**Appendix U**). Intervention group participants will complete the Follow-Up Survey Intervention (**Appendix V1**) at T6. Control group participants will complete the Follow-Up Survey Control Survey (**Appendix V2**) at T6. As a result of study extension funding, both groups will also complete surveys at T12. The T12 INT survey (**Appendix W1**) is identical to the T6 INT survey, but does not include any satisfaction items. The T12 CONT survey (**Appendix W2**) is identical to the T6 INT follow-up survey.

The timing for completing the T6 and T12 follow-up surveys is outlined below and uses the same time windows for follow-up HbA1c testing.

SURVEY VERSION	GROUP	TIMING*
Baseline	All Participants	T0
T6 Follow-up (INT)	Intervention Group	T6 (5 – 7 months [6±1])
T6 Follow-up (CONT)	Control Group	T6 (5 – 7 months [6±1])
T12 Follow-up (INT)	Intervention Group	T12 (11 – 13 months [±1])**

T12 Follow-up (CONT)	Control Group	T12 (11 – 13 months [12±1])**
----------------------	---------------	-------------------------------

* 1 month = 30 DAYS ALWAYS

** Alternatively, T12 survey windows can be manually calculated as 5-7 months **after** the completion date of a participant’s T6 follow-up activities. This revision will accommodate participants who complete their T6 activities at month 5 (earliest part of the window) and maintain a 5-7 month separation between the T6 and T12 follow-up activities.

If a participant does not complete their follow-up survey at T6 or T12, study staff can still complete it with the participant when they are next seen at a pantry or study activity. Participant surveys can also be completed over the phone if necessary.

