7.6.2 Completing surveys when participant needs to leave

At times, a participant may need to leave before administration of a survey is complete. If the participant completed approximately less than half the survey, staff should inform the participant that they will need to restart the survey and complete it at a future date.

Instructions for when a client does not start a survey or completes less than half:

- If possible, schedule a day and time to complete the survey within the next two weeks
- Verify the participant's contact information, and the information for their additional contacts (participant, friend, family member) in order to place reminder calls
- Remind client of the program benefits / incentive available once survey is completed
- Save participant ID# used to enter baseline data into ACCESS database and to start CASIC survey
 - Do NOT open the randomization envelope; do NOT assign client to a study group
- In the event the participant does not start or complete the survey within the two week period:
 - The client will be considered lost to follow-up; add note to ACCESS
 - Notify [name] that client did not start/complete survey and was not randomized
 - Do not reuse the participant ID# and destroy the randomization envelope
 - If the participant was completing a follow-up survey, notify [name] that the survey was not completed within the two-week window

Instructions for when a participant completes approximately half of the survey or more:

- Site staff can save the survey and attempt to finish the remainder with the client within two weeks
- If completing a baseline survey, open the randomization envelope with the participant for group assignment before the participant leaves the site
 - If randomized to the intervention group, provide participant with resources and first food package per study protocols
 - If randomized to the control group, provide participant with 1st incentive (\$15 gift card) and have participant sign for receipt of the gift card
- If completing a follow-up survey, provide participant with the correct incentive and have participant sign for receipt of the gift card
- Verify the participant's contact information, and the information for their additional contacts (participant, friend, family member) in order to place reminder calls
- If possible, schedule a day and time to complete the survey within the next two weeks, either in person or over the phone

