7.6.3 CASIC instructions for completing surveys at a later date

When exiting and resuming an incomplete survey perform the following:

CASIC Online:

1. Simply exit survey using upper right hand corner exit button on pop-up survey window
2. Email [name] to let her know of incomplete assessment and plans to complete or destroy
3. When resuming, click “Start assessment” and enter PPT ID as usual
4. You will be prompted to resume baseline survey, select this option
5. Complete survey as usual

CASIC Remote:

When managing an incomplete survey on CASIC Remote, the RA can select either option outlined below.

CASIC Remote surveys that are incomplete and uploaded to the server using the “upload data” button in the “synchronize subject data” tab cannot be resumed using CASIC Remote. They can only be resumed using CASIC Online, as the data no longer “lives” on the local drive after synchronization. You may resume a survey on CASIC Remote using the instructions below only if the survey data is not synchronized after exiting the survey. However, it is best practice to synchronize the subject data, incomplete and otherwise, at the end of each day. It is likely that these computers will be used for other survey administration during the timeframe that the incomplete survey remains outstanding. It is not possible to leave only the incomplete survey on the local drive and upload the other completed surveys, and it poses a risk of lost study data if surveys are not uploaded to the server in a timely manner, so it is best to upload the incomplete survey and resume using CASIC Online.

This may be less convenient for on-site administration, but since the RA will be working with the participant to re-schedule a time, they should take into account that they will need internet access to resume the survey. For this reason, it may be useful to complete the surveys by phone. In situations in which there are no other surveys on CASIC Remote on the computer in question and there is a reasonably short time period between first administration and completion of the incomplete survey, it may be appropriate to leave the study data from the incomplete survey on the local drive and resume and complete the survey using CASIC Remote.

Option 1: Synchronize subject data and resume survey using CASIC Online:

1. Simply exit survey using upper right hand corner exit button on pop-up survey window
2. Email [name] to let her know of incomplete assessment and plans to complete or destroy

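### Surveys may be done by phone, but the key suicide-intent steps in section 10.3 assume staff are beside the participant, and no step in the text establishes where a phone participant is

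*Combined protocol and SAP*

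**What the plan says.** All references are to the combined protocol and SAP (the Manual of Operations and Procedures).

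**Survey mode.** Section 4.2 asks staff to attempt follow-up testing and surveys face to face in a single encounter. Phone is the fallback. Section 7.6, where it deals with missed T6 and T12 surveys, adds: "Participant surveys can also be completed over the phone if necessary". Section 7.6.2 allows a survey that is about half done or more, baseline included, to be saved, with staff arranging to "complete the survey within the next two weeks, either in person or over the phone". Section 7.6.3, on surveys that can be resumed only with internet access, says: "For this reason, it may be useful to complete the surveys by phone".

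**Emergency steps.** Section 10.3 foresees suicidal disclosures while a survey is being given and describes the instruments as "including a standard 8-question section used to monitor the severity of depression". It applies to study activities generally and is not limited to in-person contact. When a participant states intent, staff must not leave the person alone, must ask whether a colleague may sit with them, and must call 911 and "inform operator of situation, your location, and the participant's disclosure of SI with intent". They then "Stay with client until emergency medical response arrives to evaluate participant". If the participant denies a plan but a clinician identifies intent, staff are to "follow any physician instructions, stop study activity, do not leave participant alone, and call 911 to activate the local emergency response system".

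**Contact details.** When a survey is interrupted or not started, section 7.6.2 says: "Verify the participant's contact information, and the information for their additional contacts (participant, friend, family member) in order to place reminder calls".

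**The concern.** Two parts of the manual do not meet. One authorises interviews with a participant who is somewhere else. The other gives emergency instructions that take staff and participant to be in the same place. An interviewer who hears a stated plan over the phone is told to give 911 the interviewer's own whereabouts, and has no instruction to find out the participant's.

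Stated intent is probably uncommon here, but it is foreseeable and may be fatal. Section 10.3 itself says staff may lack expertise in treating such emergencies and that a proper response is critical. Section 14.3 allows trained volunteers to give surveys. These are the people who most need steps that work as written. The moment after a disclosure is a poor time to start asking for an address, because the participant may hang up.

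**Working it through.** There is no figure in the plan to reproduce. The check sets the passages side by side.

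**1. Which surveys can be done by phone (7.6, 7.6.2, 7.6.3).** There are five survey versions: baseline, plus T6 and T12 in each of two arms (1 + 2 × 2 = 5). The four follow-up versions may be taken wholly by phone. Any of the five may have its remainder finished by phone. So there are two routes: the whole survey and the remainder.

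**2. The stated-intent steps in 10.3, read as if on a call.**

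| Step | On a call |
|---|---|
| Scripted reply | Works |
| Stop the survey | Works |
| Do not leave alone; ask whether a colleague may sit with them | Worded for presence |
| Call 911, giving the staff member's own location | Wrong location |
| Remain until responders arrive | Worded for presence |
| Page the study doctor | Works |
| Document the event | Works |

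Four work, two are worded for presence and one gives the wrong fact: 4 + 2 + 1 = 7. The three that do not carry over are those that keep the person watched and bring help. The counts describe wording, not risk. In the assessment steps of 10.3, the phone appears only as the way a clinician speaks with the participant.

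**3. Is current location established anywhere?**
- Section 5.2 requires a phone number or an address, not both.
- Section 4.1 collects two close contacts at baseline.
- The enrollment form (Appendix AM) has a mailing address, which need not be where the person is during a call.
- Section 7.6.2 re-verifies contact details in both of its branches. The half-or-more branch covers the remainder route. The branch for surveys not started or under half done mentions follow-up surveys, so it covers those whole-phone surveys that come after an unsuccessful visit. A T6 or T12 participant reached only by phone is not covered.

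Both routes are therefore partly covered for contact details. Neither has a current-location step in the supplied text.

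**4. Would the interviewer have the file at hand?** Not necessarily. Appendix AY says one laptop per site holds the Access database, and that staff other than the research assistants and project managers see only the data their task needs.

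**The case against.** The strongest reply is that ordinary judgement closes the gap. Staff must also describe the situation to 911, and a sensible interviewer would say the participant is elsewhere and stay on the line. Phone is a fallback, disclosures are likely rare, and 7.6.2 refreshes contact details. The survey instruments (Appendices U to W2), the consent form and the site procedures were not supplied, so a location prompt may already exist.

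Much of this stands. It limits the likely harm to delay, and it leaves open that some of the fix is already in place. It does not remove the point. Staying on the line is a natural substitute but is not written. Verified contact details are not a current location. Even with a prompt elsewhere, the 911 instruction in 10.3 would still name the wrong place for a call.

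Three stronger readings are tempting, and the documents do not support them:
- A reader might infer that 10.3 is written only for face-to-face contact. Four of the seven steps work on a call.
- A reader might infer that responders would be sent to the interviewer. That follows only if the text is applied literally and the description of the situation adds nothing.
- A reader might infer that contact re-verification misses whole-phone surveys altogether. It reaches those that follow a visit at which the survey was not started or was less than half done.

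**Conclusion.** The gap is real and worth closing. It is procedural and concerns participant safety; it does not touch the design or the analysis. Phone surveys are authorised, 10.3 applies to them, three of its seven stated-intent steps assume presence, and one of those gives 911 the wrong location if followed on a call. The size cannot be calculated, because the plan gives neither the share of surveys done by phone nor a disclosure rate. The likely harm is delayed help in a rare event. The conclusion rests on the supplied text only, and confidence is medium because the instruments and site procedures were not available.

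**What to change.** **Section 7.6.** At the start of each phone survey, ask for the participant's current physical location and a call-back number. Have the address and contacts on file at hand. Do not retain the location unless an event occurs.

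**Section 10.3.** Add a phone branch:
- Tell 911 that the participant is remote, and give the participant's location and number in place of the staff member's own location.
- Keep the participant on the line while a colleague or a second phone reaches 911; otherwise call back on the recorded number.
- Mark the sit-with and stay-with steps as in-person only.
- If location is refused, give 911 the address and contacts on file.
- Keep any notes from an actual event with the adverse-event record. Section 10.3 asks for detailed documentation, and Appendix AY keeps adverse-event forms for three years.

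Routine entry of location in Access is not needed; it would add stored personal data for a rare event. Keep the depression items in both modes, because depressive symptoms are a secondary outcome (13.4.3).

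**Cost.** About one minute per phone survey (an estimate; the documents give no figure), brief handling of personal data, a second phone or colleague, and possibly an IRB notification. Some participants may decline to give a location. No visit, outcome measure or analysis changes.

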10.4 Reports of Elder Abuse or Neglect

- Employ standard site-specific protocols or page [name] at [contact], or call on her cell at [contact].
- If unable to reach [name], study staff should call "911" to report situation and activate the emergency response system.
- Document event in detail; include report in MS Access database for study participants.

The primary investigator must be made aware of any emergencies involving study participants as soon as possible.

10.5 Reports of Poor Food Quality

All food banks participating in the FAITH-DM study are members of the Feeding America network and as such, must meet certain minimal compliance standards with respect to food safety and food distribution. Food banks are audited periodically by the Feeding America National Office and may also undergo periodic auditing by external entities. Food banks are required, in turn, to periodically monitor practices of their agencies.

Feeding America maintains a timely distribution of food recall information to all food sourcing personnel in the network. In addition, Feeding America provides education to all food banks on current guidance with respect to food industry use of dates for use by dates, best by dates and other practices. These practices will be reviewed with the study sites and the quality of food distributed will also be observed during project site visits.

Key information to be reviewed includes:

- Packing or manufacturing date
 - Used by manufacturers for tracking and recalls
 - Not an expiration date
- Sell-by date
 - This is a quality date
 - It tells the store how long to display the product for sale
 - The product is still safe to eat past this date
- Best-by or best if used by date
 - This is a quality date
 - It tells clients the date by which the product should be eaten for best flavor or quality
- Use-by or expiration date
 - This is the last date recommended for the product while at peak quality.
 - Most products (if not temperature controlled for safety - TCS) are still safe to eat past this date
 - Cut product (TCS foods) must be kept 41°F or below to control potential bacterial growth
 - Any other type of produce can be kept at room temperature or refrigerated; refrigeration provides extended shelf life but may affect the quality of the produce
 - Mold on produce is a spoilage indicator; mold will not give someone a food borne illness but product should be disposed of if mold is observed

In the event that any participant expresses a concern about the quality of food received, the site coordinator should determine if the concern is related to any potential food safety issues and if so, notify the food bank food sourcing management immediately so that appropriate follow-up measures can be taken. If a participant reports that he or she believes that food received through the program may have made them ill, food bank management should be notified immediately, so that they can implement appropriate procedures, and an adverse event form must be completed. [name], FANO project manager, must be notified within 24 hours to determine appropriate follow-up with the participant.

10.6 Study Related Injuries

Any study related injury is considered an adverse event and must be reported. Study related injuries may include:

- Sharps / needle stick injury and/or blood exposure
- Fainting and related injuries (e.g., falls)
- Excessive bleeding

In the event of a study related injury, staff should immediately respond to address the incident.

